1.1 Study Title

A pragmatic strategy empowering paramedics to assess low-risk trauma patients with the Canadian C-Spine Rule (CCR) and selectively transport them without immobilization.

1.2 Trial Registration and Data Set

The trial has been registered at ClinicalTrials.gov. The ClinicalTrials.gov identifier assigned to this study is: NCT02786966. Table 1 (below) contains information on the recommended items from the WHO Trial Registration Data Set (http://www.who.int/ictrp/network/trds/en/) (1, 2). When items from Table 1 are updated in this protocol, the trial registry at ClinicalTrials.gov will be updated accordingly.

Table 1. C-Spine Study Registration Data Set

Item	Information
Primary registry and trial identifying number	ClinicalTrials.gov, NCT02786966
Date of registration in primary registry	May 31, 2016
Secondary identifying numbers	N/A
Source(s) of monetary or material support	Ontario SPOR SUPPORT Unit (OSSU)
Primary sponsor	Ottawa Hospital Research Institute
Secondary sponsor(s)	none
Contact for public queries	[name], Study Coordinator, email: [contact]
Contact for scientific queries	[name], Principal Investigator, email: [contact]
Public Title	A pragmatic strategy empowering paramedics to assess low-risk trauma patients with the Canadian C-Spine Rule (CCR) and selectively transport them without immobilization.
Scientific Title	Can a strategy allowing paramedics to assess selective low-risk trauma patients with the Canadian C-Spine Rule and transport them without immobilization be safe, cost-effective, and result in significant health service benefits for patients, Emergency Medical Services, and Emergency Departments? – A Cluster Randomized Pragmatic Multicentre Trial.
Countries of recruitment	Canada (Ontario only)
Health condition(s) or problem(s) studies	Stable trauma patients with a potential neck injury requiring assessment by Emergency Medical Services (EMS)
Intervention(s)	Application of a decision rule – CCR – to determine the need for spinal immobilization
Key inclusion and exclusion criteria	Included: consecutive, alert (able to follow commands), stable (normal vital signs) patients evaluated by paramedics following acute blunt trauma (within 48 hours). Excluded: Patients with penetrating trauma, acute paralysis, known vertebral disease, those referred from another hospital and transported between facilities, and those younger than 8 years of age.
Study type	Stepped wedge, cluster randomized trial
Date of first enrolment	To be determined
Target sample size	7,200
Recruitment status	Not yet recruiting
Primary outcome(s)	Proportion of patients immobilized Proportion of patients feeling comfortable (co-primary outcome)
Key secondary outcomes	Proportion of patients with a pain score ≤ 4/10 Time from EMS arrival to ED discharge or admission to hospital Patient radiation exposure from diagnostic imaging Number of skin pressure injuries Number of missed c-spine injuries Time spent in the field by paramedics before arrival to hospital Time spend in-hospital by paramedics before transfer of care

ED length of stay

Number of subsequent ED visits within 30 days

Number of subsequent clinical/family physician visits within 30 days

Frequency of c-spine diagnostic imaging performed within 30 days

Incremental cost per one immobilization avoided

1.3 Protocol Version and History of Changes

Any changes to the protocol that are more substantive than simply the correction of typographical errors will be recorded in Table 2. The revised protocol will be given a new version number, and a summary of the revisions made to the previous protocol version will be listed. The current protocol version number and effective date will also be displayed in the footer at the bottom of each page in the protocol and should match the version number on the cover sheet and in Table 2.

Table 2. Description of Protocol Revisions

March 2016 N/A 1.2 Trial Registration and Data Set – addition of registry number Table 1 – Trial Registration Information 2.1 Background – addition of ILCOR reference 3 – clarification regarding number of sites 3.2 Eligibility Criteria – clarification of penetrating trauma, modification to stable vital signs Appendix 6 – Paramedic Data Collection Form – new version 6.1 Data Monitoring – additional information on DSMB	Protocol Version #	Effective Date	Summary of Revisions
Table 1 – Trial Registration Information 2.1 Background – addition of ILCOR reference 3 – clarification regarding number of sites 3.2 Eligibility Criteria – clarification of penetrating trauma, modification to stable vital signs Appendix 6 – Paramedic Data Collection Form – new version 6.1 Data Monitoring – additional information on DSMB	1	March 2016	N/A
Appendix 8 – addition of DSMB Terms of Reference	2	May 2016	Table 1 – Trial Registration Information 2.1 Background – addition of ILCOR reference 3 – clarification regarding number of sites 3.2 Eligibility Criteria – clarification of penetrating trauma, modification to stable vital signs Appendix 6 – Paramedic Data Collection Form – new version 6.1 Data Monitoring – additional information on DSMB Appendix 4 – Paramedic Committee Terms of Reference

1.4 Funding

This study has received funding through the Ontario SPOR SUPPORT Unit (OSSU's) IMPACT Awards competition. OSSU, which receives funding from the Canadian Institutes of Health Research and the Province of Ontario, has agreed to provide funding in the amount of \$1,456,990 for the period June 2, 2015 to September 30, 2018. The funding will be used to cover the direct costs required to implement and run this multicenter study. Indirect funding will be provided by the sponsor organization – the Ottawa Hospital Research Institute. Participating EMS Services have all agreed to provide paramedic training time for this study in-kind.

1.7 Roles and Responsibilities - Sponsor and Funder

Neither the Sponsor nor the Funder had any role in the design of this study. The Funder will be kept up-to-date on study progress and activities, but will not have any direct role in the execution, analysis, interpretation or publication of study results.

Appendix 2. Steering Committee Terms of Reference.

1.8.2 Publications Committee

Chair: [name]

Membership: to be decided

Responsibilities:

- Promote publication of study findings and activities in peer-reviewed, MEDLINE-indexed journals
- Support broad and equitable participation by study team members and investigators in presentations and publications
- Define rules and guidelines for writing group membership for manuscripts
- Review manuscript proposals, assign writing groups and prioritize publications and presentations
- Provide editorial support and timely review of presentations and publications.

Terms of Reference: will be appended to Appendix 3. Publications Committee Terms of Reference when finalized.

1.8.4 Paramedic Committee

Chair: [name], paramedic representative

Membership: one representative from each participating EMS Service and each supporting Base Hospital Program, study Principal Investigator, study support staff

Responsibilities:

- To help develop, review and approve study training materials, data collection forms and study advertisements
- To provide feedback to the Steering Committee on the EMS logistics of proposed study activities and processes
- Review and provide feedback on the main study protocol and any subsequent amendments
- Develop a strategy to communicate the study requirements, activities and study progress to each participating EMS service.

Terms of Reference: appended, please see

1.8.6 Data Safety Monitoring Board

Please see Section 6. Methods: Monitoring for details on the study Data Safety Monitoring Board.

Section 2. Introduction

2.1 Background

Problem: Ontario Emergency Medical Services (EMS) annually transport half a million patients with a potential neck (cervical/c-spine) injury, from falls or motor vehicle collisions, to local emergency departments (ED). Ninety-five percent of those patients are alert and stable and at low risk of c-spine injury. Less than 1% actually have a c-spine fracture, and even less (0.5%) have a spinal cord injury. Spinal cord injuries result from moderate to severe blunt traumas and not from minor movements occurring during transport to hospital. Regardless, current EMS practice is to transport all such trauma victims (with or without c-spine injury) by ambulance using backboards, collars, and head immobilizers. These patients stay fully immobilized until an ED bed is made available, sometimes for as long as 3 hours. This prolonged immobilization is often unnecessary and increases patient discomfort, contributes to ED crowding, prolongs EMS intervention times, and adds a heavy financial burden to our healthcare system.

Why C-Spine Immobilization of Low-Risk Patients May Be Unwarranted: Not only is immobilization often unnecessary, its potential for clinical adverse effects and discomfort are well documented (3). Chest straps used in immobilization can have a pulmonary restrictive effect, even in healthy non-smokers. Immobilization on a board leads to progressively worse pain in the head, neck, and back area, often resulting in the necessity to perform diagnostic imaging on an otherwise normal spine in the ED. The presence of a c-spine immobilization collar has been associated with hyperextension, actually causing spinal cord injury in patients suffering from ankylosing spondylitis. In addition, c-spine collars can cause neck vein compression and increased intra-cranial pressure for patients with head injury, difficulty swallowing, and local skin necrosis.

We have identified three systematic reviews relevant to c-spine immobilization. Work published by Abram in 2010 (32 studies) (3) suggested there was a growing body of evidence documenting the "risks and complications of routine spinal immobilization", and that there was a "possibility that immobilization could be contributing to mortality and morbidity in some patients." A more recent review by Sundstrom et al (220 studies) (4) concludes there is limited evidence supporting current c-spine immobilization practices, that large definitive randomized trials are lacking, that the benefit on neurological injury and spinal stability is uncertain, and that there is a growing body of opinions against the use of c-spine collars. The International Liaison Committee on Resuscitation (ILCOR) provides

international guidelines on cardiac arrest and trauma resuscitation. In November 2015, ILCOR published a recommendation not to use routine application of c-spine collars for adult and children with blunt suspected traumatic c-spine injury (based on very low quality of evidence from 29 studies) (5).

Effect on Overburdened EMS Systems, and Crowded EDs: Because trauma victims need to be seen rapidly at the hospital, paramedics are given only 15-20 minutes to evaluate and treat them in the field before transport. Even for minor trauma victims, c-spine immobilization takes greater than 5 minutes to apply, or up to 30% of the allotted field time. Unlike minor trauma victims coming to the ED by their own means of transport and commonly triaged to the waiting room area, minor trauma victims immobilized and transported by paramedics can wait up to 3 hours until an ED stretcher becomes available, also holding up the EMS crew who then become unavailable for the next community emergency. In 2013, the U.S. National Association of Emergency Medical Services Physicians took a position in favor of a judicious immobilization strategy (6).

Once on an ED stretcher, it is not unusual for these patients to remain fully immobilized for several hours until physician assessment and c-spine diagnostic imaging can be performed and interpreted. This consumes valuable time for physicians, nurses, and radiology technicians and distracts them from other urgent responsibilities. These delays compound the burden of our crowded Canadian EDs in an era when they are under unprecedented pressures. The median length of stay for a patient evaluated in the stretcher area is approximately 8-12 hours, whereas similar minor trauma victims arriving without immobilization can be evaluated and discharged in less than 4 hours.

The Canadian C-Spine Rule: We have derived, validated, and implemented the Canadian C-Spine Rule (CCR) to be used by physicians (7-9), triage nurses (10), and paramedics (11) in more than 40,000 alert and stable trauma patients. The CCR (Figure 1) directs that immobilization is unnecessary if the patient has no high-risk criteria, has at least one low-risk criterion, and can voluntarily rotate their neck 45' left and right. Physicians and nurses already use the CCR in the ED to safely remove immobilization devices without the need for imaging and with no documented adverse outcomes. We recently completed a pilot implementation study with Ottawa paramedics where selective patients were transported without immobilization. We have recruited 3,854 patients, and paramedics have identified all clinically significant injuries (100% sensitivity) without negative consequence when the CCR determined that immobilization was not required (68% specificity). Approximately 60% of immobilizations were avoided.

[figure not shown]
C-Spine Evaluation in Children: The NEXUS decision instrument for use in adults and children was validated in 2,160 children aged 8 to 17 (12) and identified all significant injuries. The CCR's performance was superior to that of the NEXUS decision instrument when prospectively compared in an adult population (13), but has yet to be implemented for use in children. A case-control study of children younger than 16 with c-spine injuries identified 8 risk factors for significant injuries, 7 of which are included in the CCR (14).

Based on information provided by our EMS stakeholders, we estimate there are ≥4,000 children aged 8 to 16 transported with immobilization each year in Ontario. In a survey of physicians, 85% stated they would use the CCR if it were properly evaluated for use in the pediatric population (15).

Rationale for This Study: Minor trauma is very common and these patients are usually transported to the ED by EMS, but rarely do they have a fracture or spinal cord damage. Current immobilization and transport practice guidelines are not evidence-based, and there is a growing body of evidence testifying to the deleterious effects and consequences of this practice on patients, EMS systems, EDs, and the

health care system. We have successfully derived, validated, and implemented the CCR for use by physicians, nurses, and, more recently, by paramedics in a pilot project. Patient groups, EMS stakeholders, ethics board members, and the Medical Advisory Committee for the Ontario Ministry of Health and Long-Term Care Emergency Health Services Branch (MOHLTC-EHS) are all supportive of this multicentre implementation evaluation study. We now need a large pragmatic study to evaluate the feasibility, benefits, and safety of implementing the CCR in geographically and socially diverse prehospital communities. We are encouraged that most EMS services would only participate in the study if we adopted a design that would guarantee, at some point, an opportunity for them to be assigned to the intervention arm and expand the scope of their paramedics' practice.

Figure 1. The Canadian C-Spine Rule Adapted for Use by Paramedics

2.2 Objectives

The overall goals and impacts of this study are to improve patient care and health system efficiency and outcomes by allowing paramedics to assess eligible low-risk trauma patients with the CCR and selectively transport them *without* immobilization to the ED.

We conservatively estimate that, in Ontario, more than 60% of all eligible trauma patients (300,000 annually) could be transported safely and comfortably, without c-spine immobilization devices. This will significantly reduce patient pain and discomfort, EMS intervention times, and ED length of stay, therefore improving access to EMS and ED care. This could be achieved rapidly and with lower healthcare costs compared to current practices (possible cost saving of \$36 per immobilization, or \$10,656,000 per year).

In addition, this project will facilitate a new paradigm in prehospital research by integrating paramedics and patients actively into the research and knowledge translation process. It will offer the added benefits of consolidating a network of EMS research partners and of facilitating future collaborative projects. It will also make innovative use of data provided by the Institute for Clinical Evaluative Sciences (ICES) to streamline and decrease the cost of conducting prehospital research, and, with the help of our new OSSU partners, foster collaborative efforts to measure and possibly correct health inequities in prehospital care. Lastly, this project could lead to the use of the CCR by paramedics from across Ontario and Canada and to immediate health care benefits/savings on a national scale.

PICOT Question: Does allowing paramedics to assess selective low-risk trauma patients with the Canadian C-Spine Rule (CCR) and transporting them without immobilization result in significant and immediate health service benefits for patients, Emergency Medical Services, and Emergency Departments, in a safe, cost-effective manner?

2.3 Trial Design

The multicentre implementation of the CCR by paramedics is designed as a stepped wedge cluster randomized trial with three steps, involving a total of 13 Ontario EMS Services. Our 36-month study will consist of a 12-month set-up and training period (Year 1), followed by the stepped wedge trial (Year 2), and a 12-month period for study completion, analyses, and knowledge translation and exchange (see Figure 2). EMS services in each step will cross from the control condition (usual care) to the intervention condition (CCR implementation) at intervals of 3 months until all communities have crossed to the intervention. Data will be collected on all eligible patients in each EMS service for a total duration of 12 months.

Figure 2: Diagram of the Study and Stepped Wedge Design

-8			Months 1-9		Months 10-12	
ar 1		Study set-up	Paramedic			
Year		ePlatform progra	ePlatform programming for EMS data collection			
		Preparation of study material and site visits				
	Step	Months 1-3	Months 4-6	Months 7-9	Months 10-12	
ır 2	1 (4 EMS services)	Usual Care	CCR	CCR	CCR	
Year	2 (4 EMS services)	Usual Care	Usual Care	CCR	CCR	
	3 (4 EMS services)	Usual Care	Usual Care	Usual Care	CCR	
		Months 1-6		Months 7-9	Months 10-12	
ar 3		Study completion		Data cleaning	Reports and	
Year		Data linkage with ICES		Data analyses	manuscripts	
					writing; KTE	

Section 3. Methods: Participants, Interventions and Outcomes

3.1 Study Setting

The study will take place in the province of Ontario. Up to 12 new Ontario Emergency Medical Services will participate. Ottawa will also participate, but only provide data for the pediatric cohort, since the CCR has already been implemented within their practice. The 12 new EMS services vary in terms of size, population served and geographical location. A list of the participating EMS Services is located in Appendix 1. C-Spine Study Team Membership, Roles and Affiliations). Each EMS Service in Ontario is affiliated with a Base Hospital. There are eight Regional Base Hospitals in Ontario which provide medical direction, leadership, and advice in the provision of prehospital emergency care. Although the Base Hospital Programs will not be participating directly in the study as separate sites, they will be assisting with start-up, implementation and follow-up. A list of the seven involved Base Hospital Programs is included in Appendix 1. C-Spine Study Team Membership, Roles and Affiliations).

3.2 Eligibility Criteria

All consecutive, alert (able to follow commands), stable patients (normal vital signs) evaluated by the paramedics employed by a participating EMS Service for potential cervical spine injury after sustaining acute blunt trauma (within 48 hours). These are patients for whom standard Ontario EMS trauma protocols usually require immobilization. As in prior CCR studies, patients will be excluded if they do not require immobilization as per the standard Ontario EMS trauma protocol, have a Glasgow Coma Scale score less than 15 or are intubated, or have unstable vital signs (systolic blood pressure < 90 mmHG; respiratory rate <10 or >24 breaths/minute). Patients will also be excluded if: their injury occurred more than 48 hours previously; they have penetrating trauma from stabbing or gunshot wound to the neck, acute paralysis, or known vertebral disease (specifically ankylosing spondylitis, rheumatoid arthritis, spinal stenosis or previous cervical spine surgery); they were referred from another hospital and transported between facilities; or they are younger than 8 years.

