3.3 Interventions

Paramedics will be trained in the use of the CCR prior to the start of the trial. We have conducted an Ottawa EMS CCR implementation pilot study and have designed our training program to address barriers identified in the pilot. The training entails one hour of education: 30 minutes of self-review of a teaching video addressing the background and scientific development of the CCR, and a 30-minute inclass teaching video reviewing the specific steps involved in using the CCR, complete with a demonstration and question and answer period with a certified trainer. Paramedics will be "certified" to clear the cervical spine by medical directive if they have: a) successfully completed the initial training sessions, and b) successfully completed (score of ≥80%) a written quiz. Paramedics failing the written quiz would be required to attend a remedial session and review all wrong answers with their certified trainer. Of note, Ottawa paramedics all successfully completed their training.

The stepped wedge trial will begin after paramedic training has been completed (see Figure 2). During the Usual Care phase, paramedics will complete the CCR data collection form for all eligible patients, but will continue to immobilize them all before transport to the receiving hospital. Once a community has crossed to the intervention CCR phase, paramedics will be permitted by medical directive to implement the CCR. Paramedics will then transport selected patients without immobilization according to the CCR. Although following the medical directive will be mandatory for paramedics, they will be encouraged and allowed to immobilize patients if they are uncomfortable with the CCR's recommendation to not immobilize them.

During the study set-up time period (Figure 2), each participating service will designate a local paramedic study champion. These individuals will be in close contact with staff at the Study Coordinating Centre and will receive further information about the study, the methodology and the implementation of the CCR. These individuals will be heavily involved in delivering the study training material at their particular location and will serve as a first point of contact throughout the implementation. Paramedics with questions about specific aspects of the CCR, or the application of the CCR for unusual scenarios will be able to communicate directly with a peer in an effort to promote adherence to the protocol.

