3.6 Sample Size

Our sample size for this study is determined mainly by pragmatic considerations: we need a large number of sites from across Ontario to evaluate safety and generalizability of implementation in this multicenter setting, while accounting for between-site differences such as size and setting. Power calculations were carried out for the stepped wedge trial. Using data from a previous study in these communities, we expect approximately 600 patients per EMS service per year (or 150 patients per 3 month time interval). A total of 12 EMS services (7,200 patients) evaluated across 4 time intervals in a stepped wedge design will provide at least 90% power to detect minimally important differences of 10% in our two co-primary outcomes using two-sided tests at the 2.5% level of significance. In particular, for our primary outcome we will have >99.9% power to detect a minimally important absolute reduction of 10% in the proportion of patients immobilized assuming a control arm proportion of 100%. For our co-primary outcome we will have 90% power to detect a minimally important increase of 10% in the proportion of patients feeling comfortable assuming a conservative control arm proportion of 50%. In these calculations, we have assumed a commonly used intracluster correlation coefficient (ICC) of 0.05, added 2 EMS services to account for variation in the number of patients across sites, and a further 2 EMS services to account for potential attrition.

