7.3 Consent

We will be seeking a waiver of informed consent from the OHSN-REB. This was the case in the previous multi-centre prehospital validation of the CCR, as well as the single-centre prehospital implementation study. The study protocol has been reviewed by the Medical Advisory Committee for the Ontario Base

Hospitals Group (MAC – OBHG). The MAC provides advice to the Emergency Health Services Branch (EHSB) of the Ontario Ministry of Health and Long-Term Care. Paramedics employed by EMS Services participating in the study will be allowed via a Medical Directive to use the CCR to evaluate eligible patients instead of the usual immobilization protocols. The Medical Directive will be drafted by the MAC-OBHG and authorized by the EHSB for the duration of the study.

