Appendix 5. Patient Committee Terms of Reference To be appended once developed and finalized.

Appendix 6. Paramedic Data Collection Form

EVALUATION OF THE SAFETY OF C-SPINE CLEARANCE BY PARAMEDICS CALL NUMBER: DATE OF CALL (YY/MM/DD): 1. INCLUSION CRITERIA (check as applicable) ALERT (GCS 15) STABLE (SBP ≥90mmHg, respiratory rate 10-24/minute) **ACUTE BLUNT INJURY (<48 hours)** Are all the inclusion criteria met? ■ NO - STOP; can't use the Canadian C-Spine Rule 2. EXCLUSION CRITERIA (check as applicable) Boarded and collared for reason other than c-spine injury Age < 8 years Penetrating trauma from stabbing or gunshot wound Acute paralysis (paraplegia, quadriplegia) Known vertebral disease (ankylosing spondylitis, rheumatoid arthritis, spinal stenosis, previous c-spine surgery) Referred from another hospital Does the patient have any exclusion criteria? ☐ YES - STOP: can't use the Canadian C-Spine Rule ■ NO - CONTINUE 3. THE CANADIAN C-SPINE RULE START HERE 1. Any ONE high-risk factor which mandates immobilization? ☐ No ☐ Yes Age ≥65 years ☐ No ☐ Yes Dangerous Mechanism* ☐ No ☐ Yes Numbness or tingling in extremities ☐ YES - STOP ■ NO - CONTINUE 2. Any ONE **low-risk** factor which allows safe assessment of range of motion? ☐ No ☐ Yes Rearended in Simple Rearend MVC** ■ NO - STOP ☐ No ☐ Yes Ambulatory at any time at scene ☐ C-SPINE IMMOBILIZATION ☐ No ☐ Yes No neck pain at scene when asked (answer "yes" if no pain) ☐ No ☐ Yes No pain during midline c-spine palpation (answer "yes" if no pain) Dangerous Mechanism: -fall from elevation ≥3 feet/5 stairs □ NO ☐ YES - CONTINUE axial load to head, e.g. diving -MVC: rollover, ejection, high speed (≥100km/h) -motorized recreational vehicles, e.g. ATV, 3. Patient voluntarily able to actively rotate neck 45° left and right when snowmobile requested, regardless of pain? -bicycle collision with object, e.g. post, car ☐ No ☐ Yes **Simple Rearend MVC Excludes: -pushed into oncoming traffic ☐ YES -hit by bus/large truck -rollover ■ NO C-SPINE IMMOBILIZATION -hit by high speed vehicle (≥100km/h) 1. According to the Canadian C-Spine Rule, would this patient require immobilization? 2. How comfortable would you be in following the Canadian C-Spine Rule for this patient? very comfortable ☐ comfortable ☐ neutral □ uncomfortable very uncomfortable 3. If you were uncomfortable, please briefly describe why: 4. Will you use the Canadian C-Spine Rule when deciding whether or not to immobilize this patient? Yes, this patient will be transported with or without immobilization according to the Canadian C-Spine Rule. ☐ No, I am choosing to immobilize this patient, despite the rule indicating immobilization is not required. 5. Was there a language barrier present that hindered your ability to apply the Canadian C-Spine Rule to this patient? 🗖 No 🗖 Yes 6. Before transfer of care to the Emergency Department, please ask your patient the following questions: i) On a scale of 1 – 10 (10 being the highest level of pain), how would you rate your pain right now? ii) On a scale of 1-10 (10 being very uncomfortable), how would you rate your comfort level right now?

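### The paramedic form omits the section 3.2 criterion that the standard protocol must require immobilization, so enrolment could differ by phase and bias the immobilization and comfort effects

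*Combined protocol and SAP*

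**What the plan says.** Section 3.2 admits alert, stable patients whom paramedics evaluate for a possible c-spine injury after blunt trauma, and adds that "patients will be excluded if they do not require immobilization as per the standard Ontario EMS trauma protocol".

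Under section 3.3, paramedics in the Usual Care phase complete the form for all eligible patients "but will continue to immobilize them all before transport to the receiving hospital". After crossover, "Paramedics will then transport selected patients without immobilization according to the CCR". Section 7.3 says that paramedics "will be allowed via a Medical Directive to use the CCR to evaluate eligible patients instead of the usual immobilization protocols". The power calculation in section 3.6 is made "assuming a control arm proportion of 100" per cent, and section 5.4 uses the same 100% as the economic comparator.

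The inclusion block of Appendix 6 lists "ALERT (GCS 15) STABLE (SBP ≥90mmHg, respiratory rate 10-24/minute" and acute blunt injury under 48 hours, then asks "Are all the inclusion criteria met". Six exclusion items follow. The one closest to the section 3.2 criterion is "Boarded and collared for reason other than c-spine injury". A failed check stops use of the rule.

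Appendix 7, as far as it can be read, records study phase, what the CCR indicated, whether and how the patient was immobilized, mechanism, times and pain medication. It does not record what the standard protocol would have required.

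Section 5.1 has staff review the paramedic documentation for compliance. Section 6.3 classes use of the rule in the wrong population as a protocol deviation for the DSMB. Section 5.4 does not say whether such cases stay in the analysis. Section 5.2 says that missed cases will not be traced.

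**The concern.** This criterion supplies the counterfactual. An immobilization can be avoided only in a patient who would otherwise have been immobilized. The 100% control proportion, the first co-primary outcome and the cost per immobilization avoided all depend on it.

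The phases give different incentives. In Usual Care, completing a form goes with immobilizing the patient, which discourages opening one for someone who would not have been boarded. In the CCR phase that link is gone. An alert, stable patient under 65 with a blunt limb injury, no neck pain, no high-risk factor and normal neck rotation passes every item on the form, clears the rule and looks like an avoided immobilization.

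Paramedics know which phase they are in. A change in who is enrolled that occurs when a service crosses over coincides with the treatment term, so the service and time-interval effects in section 5.4 cannot remove it. At stake are the size of the immobilization effect, the comfort co-primary and the cost-effectiveness ratio.

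**Working it through.** **1. Criterion against forms.** Appendix 6 has three inclusion items (alert, stable, acute blunt injury) and six exclusions (boarded for another reason, age under 8, penetrating trauma, acute paralysis, known vertebral disease, referral from another hospital). None asks whether the standard protocol requires immobilization. The boarded-for-another-reason item presupposes a boarded patient, so it cannot catch one whom nobody would have boarded. Appendix 7 has no matching field in its legible part.

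**2. The plan's own figures.** Inputs from section 3.6: 12 services, 4 intervals, 150 patients per service and interval, ICC 0.05, two-sided 2.5% level (critical value 2.241). I used the Hussey-Hughes variance with 4 services per step.
- Comfort, 50% to 60%: variance 0.55 × 0.45 = 0.2475, standard error 2.15 points. Power = Φ(10/2.15 − 2.241), about 99% with 12 services. With the 8 services left after removing the 2 + 2 added for size variation and attrition, it is 91.7% to 95.0%, depending on the step split and variance convention.
- Immobilization, 100% to 90%: standard error 0.94 points with 12 services; power above 99.9% with 8 or 12.

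The stated power of at least 90% is met. The missing item changes no stated alpha, sample size or power; the issue is bias.

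**3. Immobilization.** Let *f* be the share of CCR-phase forms from patients outside the criterion and *q* the proportion of them immobilized. Neither is in the documents. True CCR-phase immobilization is taken as 40%, from the pilot's roughly 60% avoided (section 2.1), with control at 100%.

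Apparent reduction = 100 − [(1 − *f*) × 40 + *f* × *q*].

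Extra patients in the CCR phase only, *q* = 0:
- *f* = 5%: 100 − 38 = 62 points
- *f* = 10%: 100 − 36 = 64 points
- *f* = 20%: 100 − 32 = 68 points

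At *f* = 10%, varying *q*:
- *q* = 40%: 100 − (36 + 4) = 60, no bias
- *q* = 60%: 100 − (36 + 6) = 58, a smaller effect

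Equal entry in both phases at 10%, with none of these patients immobilized in either: control 90, CCR phase 36, reduction 54. This dilution requires that section 3.3 is not followed for them in Usual Care. If they were immobilized there as instructed, control stays at 100 and the contrast is again 64.

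**4. Comfort.** Planning values are 50% and 60% (section 3.6). Let *c* be the proportion of extra patients who are comfortable (assumed).

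Apparent gain = (1 − *f*) × 60 + *f* × *c* − 50.

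At *f* = 10%, CCR phase only, *c* = 50, 60, 70, 80, 90% gives +9, +10, +11, +12, +13 points against a true +10. At *c* = 80%, *f* = 5% gives +11 and *f* = 20% gives +14. Equal entry at 10% with the same comfort in both phases gives 0.9 × 10 = +9.

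**5. Comfort with no true effect.** With CCR-phase entry only, *c* = 80% and 50% otherwise, the spurious gain is *f* × 30 = 0.6, 1.5 or 3.0 points at *f* = 2, 5 or 10%. With standard error 2.15, the rejection probability is about 3%, 6% or 20% against the nominal 2.5%.

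**6. Cost per immobilization avoided.** With the cost difference held fixed, moving the denominator from 60 to 64 multiplies the ratio by 60/64 = 0.94. The cost difference would also shift, by an amount the documents do not allow one to compute.

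**The case against.** A reader might infer that the form alone decides enrolment and that the omission certainly inflates both co-primary effects. The documents do not support that. Section 3.2 governs eligibility and already requires an evaluation for possible c-spine injury. Sections 3.3, 5.1 and 7.3 each confine the form or the directive to eligible patients. The limb-injury patient in the example fails section 3.2 whatever the form asks. Nothing in the documents shows that paramedics would open forms for such patients; the enrolment problem that section 5.2 anticipates is missed cases.

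The direction of bias is also not settled. The rule mandates immobilization for age 65 or over and for a dangerous mechanism, so some extra patients would be immobilized. The immobilization effect inflates only if they are immobilized less often than about 40%, and comfort only if they are comfortable more often than the true CCR-phase patients. On the pilot's figures, a move from 60 to 62–68 points does not alter a conclusion judged against a 10-point difference.

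Staff also receive the electronic care record and review compliance, and wrong-population use goes to the DSMB. Training content and the study manual are not in the documents and may cover the criterion.

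All of this stands against the stronger reading. It leaves the gap itself in place: compliance reviewers have no form field for the criterion, and no rule says what happens to wrong-population cases in the analysis.

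**Conclusion.** The concern holds as a risk of bias, not as a demonstrated one. A section 3.2 exclusion criterion is absent from the form that gates use of the CCR and cannot be verified from the legible second form. In an unblinded stepped-wedge trial whose Usual Care form patients are all to be immobilized, entry could therefore differ by phase.

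Inflation is the likeliest result if patients outside the criterion enter mainly after crossover and clear the rule. Its size is then 2, 4 or 8 points on a 60-point reduction at assumed shares of 5%, 10% or 20%, and 2 points on comfort at a 10% share with 80% comfortable, a fifth of the minimally important difference. Other entry patterns give no bias or dilution. The shares and the extra patients' outcomes are assumptions without a source in the documents.

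The primary conclusion is unlikely to flip. The effect size, the comfort result and the cost per immobilization avoided are what is exposed.

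**What to change.** 1. Align Appendix 6 with section 3.2. Add a mandatory item, in both phases and before the rule is applied: would the standard Ontario EMS trauma protocol require c-spine immobilization for this patient? No means not eligible.
2. Add a matching field to Appendix 7, completed from the complaint, mechanism and findings in the electronic care record, masked to phase and immobilization status where feasible.
3. Report enrolment counts and case mix (age, mechanism, CCR result) by service and period, so that a shift at crossover can be seen.
4. In section 5.4, pre-specify a sensitivity analysis restricted to patients confirmed to meet the criterion. It should not be the primary analysis. Appendix 7 holds phase and immobilization status on the same sheet, so an imperfectly masked retrospective judgement could itself exclude patients differently by phase.

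The cost is one extra form item, one field in a chart review that already takes place, slightly fewer patients, and some error in the retrospective judgement. The registration table lists the trial as not yet recruiting, so the form can still be changed before use.
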